6.4 Thrombotic Events

Investigators should perform all testing required to fully characterize arterial or venous thrombotic/vascular events. The incidence, type, and diagnostic tests used for the diagnostic confirmation of thrombotic/vascular events will be collected and reported. Because of the high rate of venous thrombotic events in patients with upper gastrointestinal malignancies, and because therapy with antiangiogenic agents has been shown to be feasible in the setting of anticoagulation in patients with upper gastrointestinal malignancies, patients who develop Grade 3-4 venous thrombotic events (deep vein thrombosis [DVT] or pulmonary embolism [PE]) may continue study therapy if the event is not considered to be life-threatening in the opinion of the investigator, the patient is asymptomatic, and/or the event can be adequately treated with low molecular weight heparin-based therapy.

Grade 3-4 arterial thromboembolic events, or any PE/DVT occurring or intensifying during anticoagulant therapy, will warrant discontinuation of study therapy.

6.5 Hemorrhagic Events

Ramucirumab therapy should be discontinued in the event of any Grade 3-4 bleeding (hemorrhagic) event.

6.6 Proteinuria

If, while on therapy, a patient has proteinuria $\geq 2+$ per a dipstick (equivalent to $\geq 100-300$ mg/dl) or routine urinalysis, ramucirumab therapy will continue as scheduled, and a 24-hour urine collection will be conducted prior to the subsequent scheduled treatment cycle. If the protein level is $< 2\text{g}/24$ hours, the patient will continue on study therapy at the same dose without interruption. If the protein level is 2 to 3 g/24 hours, study therapy for the subsequent cycle will be held for up to 2 weeks and a 24-hour urine collection will be repeated. Treatment will resume at a reduced dose level (6 mg/kg every other week) once the protein level returns to $< 2\text{g}/24$ hours. A second dose reduction (to 5 mg/kg every other week) is permitted if the protein level $> 2\text{g}/24$ hours recurs. The patient will be discontinued from the study if the protein level is $> 3\text{g}/24$ hours, if there is a third occurrence of proteinuria $> 2\text{g}/24$ hours, or if the protein level does not return to $< 2\text{g}/24$ hours within 2 weeks.

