6. TREATMENT PLAN

This is an open-label phase II study. Patients with advanced biliary cancers will be enrolled. All patients must be registered on the M. D. Anderson Cancer Center Clinical Oncology Research (CORE) system prior to initiation of treatment.

This study will enroll up to 60 patients to at MD Anderson Cancer Center. Accrual is projected to be 2.5 subjects per month. If this study proceeds to a future trial for patients with DNA repair gene of FGFR mutations, data obtained from this expanded cohort of 10 patients will be included in final analysis.

This will be an open-label, single arm study with each cycle being 14 days. Ramucirumab will be administered at 8 mg/kg intravenously on day 1 of the cycle. Restaging will be done every 4 cycles (+/- 1week). Treatment will be continued until progression unless other reasons for study discontinuation occur as listed in section 8 “Criteria for Removal from the Study.” Additionally, patients who have therapy interrupted for consolidative therapies (including, but not limited to radiation therapy, radioembolization, and chemoembolization) or at the physician’s discretion, will remain on study for survival analyses.

Table 2: Starting Dose Level

Drug	Dose	Infusion Time	Schedule (in 14-day cycle)
IV Ramucirumab	8 mg/kg	60 min (+/- 5 min)	Day 1

Dosing and Administration

The study drug will be provided by the sponsor and administered in the following order with the specified pre-medications:

- Premedication should be with an IV H₁ agonist, diphenhydramine 50 mg in NS 50 mL IV within 30 minutes prior to treatment
- Ramucirumab 8 mg/kg in NS to final volume of 250 mL IV over 60 minute on day 1 repeated every 14 days

Dose Modifications and Toxicity Management

Dose modifications and treatment delays based on observed drug-related toxicity will be performed as described below. Any toxicity associated or possibly associated with ramucirumab treatment should be managed according to standard medical practice.

Specific adverse events of concern, which may or may not be associated with ramucirumab therapy, include infusion reactions, hypertension, arterial or venous thrombotic events, bleeding (hemorrhagic) events, and proteinuria. These are specified in greater detail below.

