A cycle of therapy may be delayed up to 3 weeks to allow for weather events, patient’s personal emergencies, observation of holidays, or other unforeseen delays that the Investigator deems to be in the best interest of the patient. For any dose interruptions, re-initiation of therapy may be delayed for a maximum of 30 days to allow recovery from any toxicity. In exceptional cases where subjects are responding, re-initiation of therapy after missing > 30 consecutive days of treatment may be done on a case-by-case basis after confirmation with the Primary Investigator.

Toxicity will be graded according to the NCI CTCAE, Version 4.0 (which is available at: http://ctep.info.nih.gov/protocolDevelopment/electronic_applications/ctc.htm). For any event which is apparent at baseline, the dose modification will apply according to the corresponding shift in toxicity grade if the investigator feels this is appropriate, (e.g. if a patient has grade 1 asthenia at baseline which increases to grade 2 during treatment, this will be considered as a shift of 1 grade and treated as a grade 1 toxicity for dose modification purposes).

Dose modifications of ramucirumab will be done based on the specific toxicity. Once a dose of

any study drug has been reduced, it should not be increased at a later time. Reasons for dose modifications or delays, the supportive measures taken, and the outcome will be documented in progress notes. Growth factors may be used to treat hematologic toxicity and will not constitute a dose reduction. A maximum of a 3-week treatment delay is permitted to allow recovery of toxicities.

Table 3: Dose Levels

Dose Level	Ramucirumab (mg/kg)
0 – baseline	8
-1	6
-2	5

Hematologic Toxicity

Though myelosuppression is expected to be rare, in the event dose modifications are required at the beginning of a cycle due to hematologic toxicities, dose of ramucirumab may be adjusted as detailed below.

Table 4: Dose Modifications for Day 1 of Each Cycle (Hematologic Toxicity)

ANC		Platelets	Timing
≥ 1,500 cells/mm ³	AND	≥ 75,000/uL	Treat on time
< 1,500 cells/mm ³	OR	< 75,000/uL	Delay by 1 week intervals until recovery

Special Instructions Regarding Treatment of Chemotherapy-related Toxicity

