Dose modification or delay may occur in the setting of lower Grade toxicity if the treating physician believes that it is in the interest of a subject’s safety. Alopecia and nausea and/or vomiting that can be controlled by antiemetics do not require dose modification or interruption. No dose reduction or interruption will be required for anemia as it can be satisfactorily managed by transfusions. Dose reductions for non-hematologic toxicity should be as below.

Table 5: Dose Modifications for Ramucirumab on Day 1 of Each Cycle (Non-Hematologic Toxicity)*

Toxicity/Dose Held	Ramucirumab dose this cycle
Grade 0-2 toxicity	Same as Day 1 previous cycle
Grade 3 toxicity	Decrease ramucirumab to next lower dose level
Grade 4 toxicity	Off protocol treatment
Dose held in 2 previous consecutive cycles	Decrease ramucirumab to next lower dose level and continue throughout the rest of treatment

* Drug-specific toxicities are explained in greater detail below with appropriate modifications

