6.3 Hypertension

If a patient develops hypertension during the study, he/she should be treated with antihypertensive medications according to standard medical practice.

Grade<3

- If the hypertension is not associated with symptoms, continue ramucirumab and initiate anti-hypertensive therapy.

- If the hypertension is associated with symptoms, hold ramucirumab until symptoms resolve and initiate anti-hypertensive therapy.
- If ramucirumab therapy is held more than once for hypertension (ie, symptomatic hypertension, markedly elevated blood pressure unresponsive to anti-hypertensive therapy), the dose of ramucirumab should be reduced upon re-treatment (refer to protocol for dose and frequency). A second dose-reduction (refer to protocol for dose and frequency) should be undertaken if an additional postponement of therapy is required.

Grade 3 (systolic BP \geq 160 mmHg or diastolic BP \geq 100 mmHg; medical intervention indicated; more than one drug or more intensive therapy than previously used indicated)

- For Grade 3 hypertension not associated with symptoms, continue ramucirumab with more intensive anti-hypertensive therapy. If systolic BP remains \geq 160 or diastolic BP \geq 100 mmHg $>$ 2 weeks after initiation of additional anti-hypertensive therapy, hold ramucirumab while continuing appropriate anti-hypertensive therapy.
- If the hypertension is associated with symptoms, hold ramucirumab until symptoms resolve and initiate anti-hypertensive therapy.
- If ramucirumab therapy is held more than once for hypertension (ie, symptomatic hypertension, markedly elevated blood pressure unresponsive to anti-hypertensive therapy), the dose of ramucirumab should be reduced upon re-treatment. A second dose-reduction should be undertaken if an additional postponement of therapy is required.

Grade 4 or refractory

Patients with Grade 4 hypertension (life-threatening consequences, eg, malignant hypertension, transient or permanent neurologic deficit, hypertensive crisis; or urgent intervention indicated) or patients whose hypertension is poorly controlled ($>$ 160 mmHg systolic or $>$ 100 mmHg diastolic for $>$ 4 weeks) despite appropriate oral medication ($>$ 2 oral agents at maximum tolerated dose) will be discontinued from study therapy.

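### Section 6.6 fixes the resumption doses after proteinuria without regard to the current dose, and is not reconciled with the other reduction rules for a patient already reduced

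*Combined protocol and SAP*

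**What the plan says.** Section 6 sets the starting dose: "Ramucirumab will be administered at 8 mg/kg intravenously on day 1 of the cycle". Table 3 lists three levels: 8 mg/kg (level 0, baseline), 6 mg/kg (level -1) and 5 mg/kg (level -2). The general text on dose modifications adds that once a dose of "any study drug has been reduced, it should not be increased at a later time".

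Three places then lower the dose:

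- **Table 5 (non-hematologic toxicity).** For a Grade 3 toxicity the instruction is "Decrease ramucirumab to next lower dose level". The row for doses held in two consecutive cycles also steps down one level. A footnote refers drug-specific toxicities to the later subsections.
- **Section 6.3 (hypertension).** The dose is reduced on re-treatment if ramucirumab has been held more than once for hypertension. Then: "A second dose-reduction should be undertaken if an additional postponement of therapy is required".
- **Section 6.6 (proteinuria).** After a first result of 2 to 3 g/24 hours and recovery below 2 g: "Treatment will resume at a reduced dose level (6 mg/kg every other week". On recurrence above 2 g: "A second dose reduction (to 5 mg/kg every other week) is permitted". The patient is discontinued at a level above 3 g, if recovery takes longer than two weeks, or "if there is a third occurrence of proteinuria" above 2 g.

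Table 5 states a step relative to the current level. Section 6.3 calls for reductions without giving figures. Only section 6.6 attaches an absolute dose to each occurrence.

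**The concern.** Section 6.6 reads as though every patient with a first qualifying proteinuria result is still at 8 mg/kg. Nothing in the protocol ensures this, because reductions for other toxicities draw on the same three levels. For a patient with an earlier reduction, the figure in 6.6, its description as a reduction and the general no-increase rule may not all be satisfiable together.

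What is at stake is the dose given to a patient with more than one drug-related toxicity. Two clinicians following the protocol could resume such a patient at different doses, each with a passage to cite. Hypertension and proteinuria both appear among the Grade 3 toxicities reported for the initial cohort (Background, initial data with ramucirumab in biliary cancer), and urinalysis is scheduled on day 1 of every cycle. The combination is therefore possible, although the documents do not report that it occurred.

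**Working it through.** No sample size, power or event count is involved, and the plan states no figure to reproduce. The check lists every dose at which a patient could meet section 6.6.

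**Inputs.** Levels 8, 6 and 5 mg/kg (Table 3); first resumption dose 6 mg/kg and second 5 mg/kg (section 6.6); one level down for Grade 3 toxicity or repeated holds (Table 5); up to two reductions for hypertension (section 6.3); no later increase (section 6, general text).

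**Step 1: can a patient already be reduced?** Yes. One Table 5 step, or one 6.3 reduction after more than one hold, takes 8 to 6. A second step takes 6 to 5.

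**Step 2: first proteinuria event, 6.6 read literally.** Change = (6 - current dose) / current dose.

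| Current dose (mg/kg) | 6.6 dose | Change | One level down in Table 3 |
|---|---|---|---|
| 8 | 6 | (6 - 8)/8 = -25% | 6 |
| 6 | 6 | (6 - 6)/6 = 0% | 5 |
| 5 | 6 | (6 - 5)/5 = +20% | none listed |

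**Step 3: compare with the other statements.**

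- At 8 mg/kg all provisions agree.
- At 6 mg/kg the dose does not change. The no-increase rule is respected. Whether the sentence's description of a reduction is met depends on whether it means reduced from baseline or from the current dose.
- At 5 mg/kg the figure is above the current dose. It cannot be a reduction in either a further or a maintained sense, and following it would breach the no-increase rule.

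**Step 4: second proteinuria event.** A patient at 6 mg/kg after a first proteinuria event who is then reduced to 5 mg/kg for hypertension has a second proteinuria result. The 6.6 dose is 5 mg/kg, and (5 - 5)/5 = 0%. The text calls this a second reduction, but the current dose does not change.

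**Step 5: does any passage settle it?** The Table 5 footnote sends proteinuria to section 6.6, which is where the difficulty lies. Section 6.6 neither mentions a prior reduction nor claims an exception to the no-increase rule. No passage gives an order of precedence.

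**Separate check, lowest level.** Table 5 gives 8 to 6 and 6 to 5, but no step from 5. Section 6.6 has its own end point in discontinuation at a third occurrence. Section 6.3 discontinues Grade 4 or refractory hypertension but does not address a further hold at 5 mg/kg.

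**The case against.** The strongest reply is that the protocol should be read as a whole. The no-increase rule is general and 6.6 makes no exception to it, so a reader might infer from the 6 mg/kg figure that the protocol orders an increase from 5 mg/kg, but the documents do not support that. This stands. The instructions for that patient cannot be reconciled as written, which is different from an instruction to increase. It does not remove the point, because the reader must still discard one explicit statement and is not told which.

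Second, Table 3 labels 8 mg/kg as baseline, so resuming at 6 mg/kg can fairly be called a reduced level for a patient already there. This also stands: that case is an ambiguity and breaches no stated rule.

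Third, the situation may be rare. Every patient starts at 8 mg/kg, where 6.6 works. By the hypertension route, reaching 5 mg/kg takes more than one hold, a reduction, a further postponement and a second reduction, all before a first 2 to 3 g result. Median PFS in the initial cohort was 2.73 months, about six cycles (2.73 x 30.4 / 14 = 5.9, taking 30.4 days per month). The Background reports 9 Grade 3 toxicities in 42 treated patients, without saying that any patient had two of them or was dose-reduced. So frequency is unknown, and no claim about which patients face the greatest risk can be supported.

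Fourth, a reader might infer that Table 5 calls for a level absent from Table 3. It names no such level. The gap arises only for a patient already at 5 mg/kg. It is narrowed by the discontinuation rules for Grade 3 or 4 infusion reactions, arterial events and bleeding, and for perforation. Section 8 also leaves unacceptable adverse events to the treating physician's judgment. That gap would not merit a finding alone.

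**Conclusion.** The point holds as an internal inconsistency in the dosing text. Section 6.6 fits the rest of the protocol without qualification at only one of the three Table 3 levels. At 5 mg/kg its figure is 20% above the current dose and conflicts both with its own wording and with the general rule. At 6 mg/kg it gives no further reduction, and the wording is open to two readings. These are counts of dose levels, not of patients, and say nothing about how many patients are affected.

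The conclusion assumes that reductions under Table 5 and section 6.3 follow the Table 3 levels, and that a patient reduced for one toxicity can later have a first qualifying proteinuria result. The documents permit both. Nothing in them shows an effect on the PFS analysis, the sample size, the futility rule or the toxicity boundaries. The missing instruction at the lowest level in Table 5 and section 6.3 is a separate, minor point.

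**What to change.** Reconcile the general no-increase rule in section 6, Table 5, section 6.3 and section 6.6, so that a patient already reduced for another toxicity who then meets 6.6 has one consistent instruction, for both the first and the second proteinuria event. The documents should make clear which provision governs. The dose and the rule are for the clinical team to decide; this review proposes neither.

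In the same edit, clarify how Table 5 and section 6.3 apply to a patient already at the lowest Table 3 level.

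The cost is a wording amendment to those passages, with no added procedures. It has prospective value for any patient still to be treated, including those in the ten-patient expanded cohort.

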6.7 Gastrointestinal Perforation

An infrequent incidence of gastrointestinal perforations has been associated with some antiangiogenic therapeutic agents, most specifically in the context of colorectal cancer (treated with combination regimens including anti-VEGF antibodies and cytotoxic chemotherapy) and in advanced ovarian cancer. These events may be associated with

extensive abdominal/peritoneal disease burden. Gastrointestinal perforation has been reported from clinical studies investigating ramucirumab. The incidences of these events to date and presence of significant comorbidities and risk factors preclude any definitive association with ramucirumab, although ongoing surveillance remains essential. Three gastrointestinal perforations have been reported in Phase 2 studies investigating ramucirumab (overall incidence, 0.8% of patients). Two of these events occurred on the ovarian cancer study (CP12-0711) and one on the prostate cancer study (CP18-0601). All three cases were reported as SAEs; the events on the ovarian cancer study included a Grade 4 colonic perforation (considered probably related by the investigator) and a Grade 5 bowel perforation (considered unrelated); the perforation occurring on the prostate cancer study was a Grade 3 rectal perforation (possibly related). Each of these events was characterized by extensive abdominal and/or pelvic tumor burden, including an obstructing lesion immediately distal to an area of dilated intestine and perforation (Grade 5 event on the ovarian cancer study), a diffusely infiltrated peritoneum (Grade 4 event on the ovarian cancer study), and prior pelvic radiation (Grade 3 event on the prostate cancer study). Ramucirumab should be permanently discontinued in the event of a gastrointestinal perforation.

Concomitant Medications

Supportive care, including but not limited to anti-emetic medications, may be administered at the discretion of the Investigator. Erythropoietin and G-CSF may be administered at the discretion of the investigator, consistent with institutional guidelines.

7. EVALUATION DURING STUDY

- Patients must begin Cycle 1 within 14 days of signing the informed consent document and after the screening assessments. Treatment will be administered by qualified and trained site personnel in a hospital, clinic, or other out-patient setting appropriate for chemotherapeutic infusions. All assessments should be performed within 72 hours of each specified time parameter, with the exception of Cycle 1 in which assessments must be conducted within 24 hours (except those noted), or if medical or scheduling conditions require a delay. Request of 20 unstained tumor slides of 5 to 10 microns thick will be sent at enrollment.

Day 1 of each cycle (except where noted)

- Inclusion/exclusion review (Cycle 1 only)
- Directed physical exam
- Vital Signs
- Measurement of weight (kg) and BSA calculation prior to dosing.
- ECOG Performance Status (see Appendix 1)
- Hematology: CBC with differential and platelet count

- Serum chemistries: glucose, creatinine, BUN, total bilirubin, AST, ALT, alkaline phosphatase albumin, LDH, total protein, and electrolytes (sodium, potassium, phosphorus, chloride, CO₂, magnesium, calcium). In patients with known Gilbert’s syndrome, it is recommended to perform a direct bilirubin and indirect bilirubin.
- CA 19-9
- Urinalysis
- AEs using the NCI CTCAE (<http://ctep.info.nih.gov>)
- Concomitant medication notation

Prior to Cycles 4, 8, 12, etc.

- In order to more precisely determine time to progression, the investigator is encouraged to obtain radiological assessments earlier if there is a strong clinical suspicion of disease progression, in order to either confirm or refute the clinical impression.
- Reassessment of the extent of tumor should be made by the same imaging methods used to establish baseline tumor measurements.

Table 7: Study Assessments (treatment cycle is 14 days)

Evaluation or Procedure	Screening ¹	Study Treatment	End of Treatment Evaluation ¹¹	30-day Post-Treatment Evaluation ¹² /Long Term Follow-up
		On or before Day 1 of each cycle		
Informed consent	X			
Medical History	X			
Physical Examination	X	X ^{3,4}	X	
Inclusion/Exclusion criteria	X			
Height	X			
Weight	X	X ^{3,4}	X	
Vital Signs (Blood Pressure)	X	X ^{3,4}	X	
ECOG Performance Status	X	X ^{3,4}	X	
Hematology ¹⁰	X	X ^{3,4}	X	
Biochemistry ¹⁰	X	X ^{3,4}	X	
Urinalysis ¹⁰	X	X ^{3,4}	X	
Serum or urine pregnancy test (for females of child-bearing potential)	X			
Tumor Tissue Collection	X ²			
Toxicity assessment	X	X ^{3,4}	X	X ⁸
Diagnostic Imaging for Tumor Assessment, preferably dual-energy CT ⁷	X	Every 4 cycles ⁵	X ⁶	X ⁶
Survival				X ⁹

1. Informed consent must be obtained before any evaluations are initiated. Diagnostic imaging studies must be completed within 28 days prior to first day of study treatment. All other baseline evaluations, except for height (which can be obtained at

any time prior to enrollment), must be completed within 7 days prior to first dose of study drug.

2. When patients are enrolled, we will collect their pre-existing tissue biopsies, if available, for testing. The Oligo GEArray® Human Angiogenesis Microarray profiles the expression of 113 genes involved in modulating the biological processes of angiogenesis and will be investigated for correlation with outcome, include PFS. Archival tumor biopsy specimens will be used. This investigation will be performed at MD Anderson Core Facility.
3. For Cycle 1, baseline evaluations will suffice as they are performed within 7 days prior to first dose of study drug (except for imaging studies which are performed within 28 days prior).
4. Within 72 hours prior to start of the cycle (except for Cycle 1 as noted above).
5. Imaging should be obtained every 4 cycles (+/- 1week). Evaluations earlier than every 4 cycles are allowed if, in the investigator's opinion, this evaluation is in the patient's best interest.
6. The end of treatment imaging does not have to be repeated if recent imaging has been completed within 4 weeks. For patients discontinued from the study for reasons other than progression, it is recommend to perform every 12 weeks (+/- 5 week) after the End of Treatment Evaluation visit until documentation of progression or for 12 months after their first dose of study drug, whichever comes first, if no other anti-cancer treatment is given.
7. CT of the chest, abdomen, and pelvis. MRI may be used in cases where it is felt to be unsafe to perform CT secondary to patient's history of dye allergy, or if the tumor is not adequately seen on CT for the purposes of this study.
8. Treatment-related adverse events occurring during study treatment or within 30 days (window of 28-35 days allowed) after the last administration of study drug(s) will be followed until resolution or stabilization. If the patient is unable or unwilling to return to M. D. Anderson for this assessment, the patient will be contacted by phone for this assessment.
9. Every 3 months (+/- 5 weeks) from Post-Treatment Evaluation.
10. Hematology: complete blood count with differential. Chemistry: glucose, creatinine, BUN, total bilirubin, AST, ALT, alkaline phosphatase, albumin, LDH, total protein, and electrolytes (sodium, potassium, phosphorus, chloride, C02, magnesium, calcium). Tumor markers (CA19-9) as indicated. Tumor markers are performed every 2 cycles. In patients with known Gilbert's syndrome, it is recommended to perform a direct bilirubin and indirect bilirubin.
11. Within 10 days of decision to discontinue study treatment.
12. At 28-45 days from last dose of study medication.

